8.5.4. Urinary Retention

Analyses to further characterize the AE of preferred term ‘urinary retention’ will be undertaken.

Time to onset of first urinary retention will be summarized and analysed according to “Study Specific Safety Analyses for Time to Event data” in 8.5.2. This will be undertaken for only TC1.

Duration of urinary retention will be summarized by treatment group (and total for GTC1, GTC2, GTC3 and Overall) and study phases (TC1, GTC1, GTC2 and GTC3) and listed. Duration of urinary retention is calculated cumulatively as the same manner as described in Section 8.5.2.

8.5.5. Ultrasound

The listing of kidney and bladder ultrasound data will be prepared.

Listing will display the date of morphology, Yes / No for “Was the subject detected kidney stone?” and Yes / No for “Was the subject detected bladder stone?” at least.

8.6. Patient Profile Listings

Listing for patient profiles will be produced if one of the events is reported below.

CV EVENTS (ARRHYTHMIAS, CONGESTIVE HEART FAILURE, CEREBROVASCULAR EVENTS STROKE AND TRANSIENT ISCHEMIC ATTACK, DEEP VEIN THROMBOSIS (DVT) /PULMONARY EMBOLISM (PE), MYOCARDIAL INFARCTION/ UNSTABLE ANGINA, PERIPHERAL ARTERIAL THROMBOEMBOLISM, PULMONARY HYPERTENSION, REVASCULARISATION, VALVULOPATHY) and DEATH

CONFIDENTIAL

204947

9. OTHER ANALYSIS

Any analyses of neutralizing antibody measurement will not be described in this RAP.

CONFIDENTIAL

204947

11. APPENDICES

11.1. Appendix 1: Protocol Deviation Management and Definitions for Per Protocol Population

11.1.1. Exclusions from Per Protocol Population

A subject meeting any of the following criteria will be excluded from the Per Protocol population:

Number	Exclusion Description
01	Eligibility Criteria Not Met: Subjects who have deviated from any of inclusion or exclusion criteria
02	Excluded Medication (medication excluded by the protocol was administered) : Subjects who have taken any of prohibited medication during the study.
03	Excluded Medication (device excluded medication deviation) : Subjects who have taken any of prohibited device during the study
04	Excluded Medication (other excluded medication deviation) : Subjects who have taken any of prohibited procedure during the study
05	Wrong Study Treatment/Administration/Dose: Subjects who have taken wrong study treatment

Exclusions from the Per Protocol population which are not considered to be deviations:
After the process of assessment windows for efficacy analyses (see section 11.3) is applied, the subject who has the incomplete 3-day diary [1] data (including no data of 3-day diary) at week 12 of TC1 will be excluded from the Per Protocol population.

[1] Incomplete 3-day diary is defined as the diary which does not have 3 valid diary days.
Refer to 11.6.2 for valid diary day.

CONFIDENTIAL

204947

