#### 4.2. Treatment Arms and Duration

This study consists of a Screening phase (within 28 days period before first treatment), a Treatment phase 1 (double-blind treatment phase: 12 to 48 weeks period after first treatment), and a Treatment phase 2 (open-label treatment phase: 12 to 36 weeks period after first treatment). The duration of overall treatment phase is 48 weeks.

Following the Screening phase, patients meeting the eligibility criteria will be randomly assigned by the registration center to one of the 2 treatment arms (either 100 U GSK1358820 or placebo) in a ratio of 1:1. Subsequently, in Treatment phase 1, patients will receive single treatment with the allocated study drug (20 injections each of 0.5 mL) which will be injected into the detrusor of the bladder. At the randomization, patients will be stratified according to the number of urinary urgency incontinence episodes reported prior to initiation of treatment phase 1 (Week 0),  $\leq 9$  or  $\geq 10$  episodes, over the consecutive 3-day diary completed during the screening phase.

Subjects who meet the criteria for re-treatment (referred to the section 5.3 Re-treatment criteria) between 12 to 36 weeks after 1st treatment can enter to Treatment phase 2 to receive re-treatment (GSK1358820 100 U). Patients are permitted to receive re-treatment until up to 36 weeks after 1st treatment and at most 2 times (Note: a minimum of 12 weeks need to be elapsed since previous study treatment). Subjects who did not receive re-treatment will remain in Treatment phase 1 and continue to visit at the scheduled study visits. Patients who complete the evaluation at 48 weeks after 1st treatment are regarded as the patients who complete the study, regardless of whether the subject was re-treated or not.

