### **6.9.2. Prohibited Medications and Non-Drug Therapies**

Use of following medications or therapy is prohibited during the Screening phase, Treatment phase and given period by exclusion criteria.

- Administration of botulinum toxin other than the study drug
- Immunization to botulinum toxin
- Treatment of symptoms of OAB including nocturia (anticholinergics, beta-3 adrenergic receptor agonist) or any other medications or therapies used for the treatment of symptoms of OAB
- Intravesical pharmacologic agent for OAB symptom (e.g., capsaicin or resiniferatoxin)
- Use of electrical stimulation and neuromodulation devices (implanted and external) for the treatment of OAB
- Cholinesterase inhibitor for the treatment of urinary disturbance

The following medications are prohibited for a minimum of 3 days (or longer according to the clinical judgment of the investigator) prior to any study treatment and must not be recommenced until the day following treatment.

- Anticoagulant medications (e.g., warfarin and other coumadin derivatives)
- Antiplatelet medications (e.g., clopidogrel and aspirin [including low dose])
- Any other medications with anticoagulative effects (e.g., non-steroidal anti-inflammatory drugs)

Note: Low molecular weight heparins (eg, enoxaparin) are permitted up to 24 hours prior to study drug treatment according to the clinical judgment.

Use of following medication is to be avoided for 8 weeks after study treatment. Patients requiring following medications during the trial are required to have any study treatment delayed until the following therapy is completed.

- Aminoglycoside antibiotics
- Curare-like agents (e.g., rocuronium)

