### **Per-Protocol (PP)**

The PP Population will be defined as the subset of subjects in the FAS who do not have any major protocol violations. Details will be provided in the Reporting and Analysis Plan (RAP). The PP population will be only used to analyze until week 12 after first treatment, because the objective to use the PP population is to check the robustness of the primary and secondary efficacy endpoints.

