4. ANALYSIS POPULATIONS

Population	Definition / Criteria	Analyses Evaluated
Screened	
 • Comprise all screened subjects 	
 • Study Population
Enrolled	
 • All participants who passed screening and entered the study. Included are: only Randomized Participants. Note screening failures (who never passed screening even if rescreened) are excluded from the Enrolled population as they did not enter the study. 	
 • Study Population
Full Analysis Set 1 (FAS1)	
 • Comprise all randomized subjects who have at least 1 post-baseline efficacy assessment. • This population will be based on the treatment to which the subject was randomized (this will be applied to FAS2 and FAS3). • Any subject who receives a treatment randomization number will be considered to have been randomized. 	
 • Study Population • Efficacy for the TC 1 (double blind phase)
Full Analysis Set 2 (FAS2)	
 • Comprise all randomized subjects who have at least 1 post-2nd treatment efficacy assessment after 2nd treatment. 	
 • Efficacy for the TC 2
Full Analysis Set 3 (FAS3)	
 • Comprise all randomized subjects who have at least 1 post-3rd treatment efficacy assessment after 3rd treatment. 	
 • Efficacy for the TC 3
Per-Protocol	
 • Comprise subjects in the FAS who do not have any major protocol violations. • Protocol deviations that would exclude subjects from the PP population are defined in Section 4.1 (Protocol Deviations) and Appendix 1 (Protocol Deviation Management and Definition for Per-Protocol Population). 	
 • Efficacy for the TC 1 until week 12 after 1st treatment
Safety for double blind phase (SPDB)	
 • Comprise all subjects who receive at least one dose of study treatment. • This population will be based on the treatment the subject actually received (this will be applied to all safety population). 	
 • Safety for the TC 1 (double blind phase)

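### Per-protocol exclusions for prohibited medication, devices and procedures have no Week 12 limit, so events up to about Week 24 can remove subjects from a Week 12 analysis

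*SAP*

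**What the plan says.** SAP 11.1.1 lists the deviations that exclude a subject from the PP set. Rows 02, 03 and 04 read "Subjects who have taken any of prohibited medication during the study", "Subjects who have taken any of prohibited device during the study" and "Subjects who have taken any of prohibited procedure during the study". The wording is the same in both versions of the plan, April and July 2018.

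The PP set has a narrower use. Protocol 9.3.1 states: "The PP population will be only used to analyze until week 12 after first treatment". The SAP section 4 table gives its use as "Efficacy for the TC 1 until week 12 after 1st treatment".

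The prohibitions run much longer. Protocol 4.2 states: "The duration of overall treatment phase is 48 weeks". For OAB drugs and the other listed therapies, Protocol 6.9.2 states: "Use of following medications or therapy is prohibited during the Screening phase, Treatment phase and given period by exclusion criteria". A second list, covering anticoagulant, antiplatelet and similar drugs, begins "The following medications are prohibited for a minimum of 3 days" and applies before every study injection, so each re-treatment opens a new window in which a deviation can occur.

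**The concern.** A drug taken after the Week 12 diary was completed cannot have affected that diary. As worded, it still removes the subject from the Week 12 PP analysis, so membership of the set is conditioned on later events.

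Those events may not be independent of the result. A subject doing badly at Week 12 has more reason to resume OAB medication. Such a subject is also more likely to be re-treated, because Protocol 5.3 requires a patient request and persisting urgency incontinence, and re-treatment brings further medication restrictions. If the drug works, more of these subjects would be on placebo. Dropping them would then select on outcome, to different degrees in the two arms.

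Protocol 9.3.1 keeps the PP set to check robustness, and SAP 7.1.3 calls the PP analysis the sensitivity analysis for protocol compliance. If it mixes non-compliance before Week 12 with selection on later events, a gap between the FAS1 and PP results is hard to interpret.

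**Working it through.** **1. Time windows side by side**

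| Item | Window | Source |
|---|---|---|
| PP exclusion, rows 02–04 | Whole study | SAP 11.1.1 |
| PP exclusion, incomplete diary | TC1 Week 12 only | SAP 11.1.1 |
| Use of the PP set | To Week 12 | Protocol 9.3.1; SAP 4 |
| Prohibited medication as intercurrent event | To Week 12 | SAP 7.1.4 |
| PP efficacy tables (2.2, 2.4, 2.7, 2.17, 2.19, 2.22) and PP exclusion table (1.7) | Interim report only | SAP Appendix 10 |
| Deviation records at the interim | Start date up to the data cut date, about Week 24 | SAP Appendix 13 |

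The SAP applies two windows to the same event, and within 11.1.1 the diary rule is limited to Week 12 while rows 02–04 are not. Read literally, (48 − 12)/48 = 75% of the exclusion period falls after Week 12. With the interim cut it is about (24 − 12)/24 = 50%.

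**2. The plan's own figures**

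The documents give no figure for the PP set. The design assumptions in Protocol 9.2.1 are differences of −1.79 episodes/day and 30 mL, SDs of 3.5 and 70, and 120 per arm. They reproduce by two-sample t-test (238 df, two-sided 5%):

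- Incontinence: noncentrality 1.79/(3.5 × √(2/120)) = 3.96, power 97.6% (stated 98%).
- Volume voided: 30/(70 × √(2/120)) = 3.32, power 91.1% (stated 91%).
- Joint: 97.6 + 91.1 − 100 = 88.7% (stated 89%).

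I use −1.79 and 3.5 below.

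**3. Possible size of the selection effect**

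Let z be the Week 12 change standardised within arm, positive meaning worse. Assume that the probability of a late exclusion is p(z) = expit(logit(p₀) + b·z), with p₀ the probability at the arm's mean response and b = 0.5 or 1 (odds ratio about 1.6 or 2.7 per SD). The mean of the retained subjects then improves by

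s = 3.5 × E[z·p(z)] / (1 − E[p(z)]),

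and the PP difference becomes −1.79 + (s_placebo − s_active).

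Example with b = 1:

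- Placebo, p₀ = 10%: E[p] = 0.134 and E[z·p] = 0.103, so s = 3.5 × 0.1033/0.8661 = 0.42.
- Active, p₀ = 5%: E[p] = 0.073 and E[z·p] = 0.062, so s = 3.5 × 0.0624/0.9273 = 0.24 (0.235 unrounded).
- Shrinkage: 0.417 − 0.235 = 0.18, or 10% of 1.79.

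| p₀ placebo / active | b = 0.5 | b = 1 |
|---|---|---|
| 10% / 5% | 0.09 (5%) | 0.18 (10%) |
| 15% / 5% | 0.18 (10%) | 0.34 (19%) |
| 5% / 3% | 0.04 (2%) | 0.08 (5%) |
| Equal rates | 0 | 0 |
| No link to outcome (b = 0) | 0 | 0 |

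**4. Cross-check without the logistic model**

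If excluded subjects are k SD worse than their arm's mean, the shrinkage is 3.5k × [p_P/(1 − p_P) − p_A/(1 − p_A)]. With 10% placebo and 5% active this is 3.5k × (0.1111 − 0.0526) = 0.205k. That gives 0.10 at k = 0.5 and 0.20 at k = 1, close to the first row of the table.

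**The case against.** A reader might infer that events up to Week 48 distort the PP result. The documents do not support this. The PP efficacy tables are scheduled only at the interim, and later deviations are cut from those records. The reach is about Week 12 to Week 24, which still covers the re-treatments at Weeks 12 and 18 that SAP 3.1 anticipates.

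A reader might also take 10–19% as the expected bias. That range leaves out the mildest corner of its own assumptions (10%/5% with the weaker slope), which gives 5%. None of the exclusion rates comes from the documents, and SAP 7.1.4 already treats 10% use of prohibited medication by Week 12 as many subjects. More late use on placebo is plausible but not documented. Poor responders in either arm can ask for open-label active treatment from Week 12, which is an alternative to prohibited OAB drugs and does not itself exclude them from the PP set.

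The re-treatment route is narrower than it looks. The day-of-re-treatment criteria in Protocol 5.3 already require drugs with anticoagulative effects to have been stopped, so such a deviation needs a site error. A re-treatment that follows a Week 24 qualification visit may also fall after the data cut.

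The consequences are limited. FAS1 is primary, the PP analysis is exploratory, and under the assumed direction the bias is toward no difference, so it does not create false support for efficacy.

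Finally, the Protocol Deviation Management Plan cited in SAP 4.1 is not among the documents and might set a time limit. It cannot be relied on to override the SAP's own PP definition, which sets none.

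These points reduce the reach and the size. They do not remove the mismatch in rows 02–04.

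**Conclusion.** The point holds as an inconsistency between the PP exclusion window and the use of the PP set. It does not depend on any assumed rate. As scheduled, prohibited medication, device or procedure events between Week 12 and about Week 24 can remove valid Week 12 data.

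The effect on the PP difference is uncertain: 0.09–0.34 episodes/day (5–19% of 1.79) under the larger assumed rates, 0.04–0.08 under the smaller ones, and none with equal rates and the same outcome link in both arms, or with no link to outcome. It would be an attenuation. A reader should not infer that the primary result is biased, because FAS1 does not use these exclusions.

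One further consequence is that Table 1.6, which counts the PP set, is reported at both interim and final. Under the current wording the PP count could differ between the two reports.

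**What to change.** In SAP 11.1.1 rows 02–04, replace *during the study* with *on or before the TC1 Week 12 assessment and before any 2nd treatment*. This matches the window in SAP 7.1.4. The reference date exists for every subject who can remain in the set, because anyone without a complete Week 12 diary is already excluded.

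Limiting row 05 (wrong study treatment) to the first treatment is an optional consistency edit. That row has no whole-study wording, and the argument above does not rest on it.

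The cost is one line of SAP text and a date condition on the deviation flag. The PP set can only stay the same or grow, and the primary analysis does not change.

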11.2. Appendix 2: Schedule of Activities

11.2.1. Protocol Defined Schedule of Events

Table 2 Time and Events Table (Screening to Treatment phase 1)

	Screening		Treatment phase 1									Withdrawal
			All subjects				If subject was not re-treated					
Week (After 1st treatment)	Within 28 days	0	2	6	12	18	24	30	36	42	48 (Study exit)	
Window			± 3 d	± 7 d	± 7 d	± 7 d	± 7 d	± 7 d	± 7 d	± 7 d	± 7 d	
Patient characteristics etc.												
Informed consent	X											
Medical history / demographics	X	X ^a										
Inclusion / exclusion criteria	X	X ^a										
Neutralizing antibody	X ¹											X
Efficacy												
Check of bladder diary ^b		X ^a	X	X	X	X	X	X	X	X	X	X
KHQ, OABSS		X ^a		X	X	X	X	X	X	X	X	X
TBS			X	X	X	X	X	X	X	X	X	X
Safety												
Adverse events ^c	X	X	X	X	X	X	X	X	X	X	X	X
Physical exam	X											X
Height, Weight	X	X ^a										X ^d
Vital signs	X		X	X	X	X	X	X	X	X	X	X
ECG	X											X
Clinical laboratory (hematology and blood chemistry)	X											X
HBsAg and HCVAb (for subjects who receive or plan to receive immunosuppressants)	X											X
Urinalysis (dipstick)	X	X ^a	X	X	X	X	X	X	X	X	X	X
Urinalysis (clinical laboratory) /	X	X ^a	X	X	X	X	X	X	X	X	X	X
Urine culture / sensitivity ^e	X											X
PVR	X ^f		X	X	X	X	X	X	X	X	X	X
Ultrasound (kidney / bladder)	X											X
Urine cytology	X											X
PSA (Only male)	X											X
Urine pregnancy test (Only females of reproductive potential) ^g	X	X ^a	X	X	X	X	X	X	X	X	X	X
Investigational product												

CONFIDENTIAL

204947

Treatment of antibiotic ^h		X			X	X	X	X	X			
Treatment of investigational product		X										
Confirmation of qualification for re-treatment criteria ^{ij}	X ^k	X	X	X	X X	X X	X X	X X	X X	X	X	X
Concomitant meds / therapies												

d = day (s)

- (a) Performed prior to treatment
- (b) Bladder diary must have been completed for any 3 consecutive days in the week prior to the visit (for screening phase only, it could have been completed for 3 consecutive days at any time within 28 days). The volume voided is recorded by subjects for one 24-hour period during the 3 day diary collection period.
- (c) Only serious adverse events assessed as related to study participation or GSK product will be recorded from the time when a subject consents.
- (d) Measured only body weight
- (e) Urine culture and sensitivity is performed by the central laboratory when urinalysis (dipstick) results were suggestive of a urinary tract infection
- (f) Could be performed during the screening phase excluding diary data collection days
- (g) If the result of urine pregnancy is suspicious, investigator (or sub-investigator) is able to conduct serum pregnancy test by central laboratory.
- (h) First dose to be administered 1 (approximately 24 hours) to 3 days prior to study injection and continued for 1 to 3 days post injection (including the day of injection)
- (i) If qualification for re-treatment criteria was met, the patient will undergo the exams specified in Table 2, column marked "If qualification for re-treatment criteria was met".
- (j) Subjects who are not re-treated will remain in treatment phase 1 and continue to visit at the scheduled study visit.
- (k) Patients must have stopped medication (i.e.: anticholinergic and beta-3 adrenergic receptor agonist indicated for patients with OAB, or other medications) or therapies for OAB for at least 7 days prior to start of screening procedures
- (l) Samples may be collected during the screening period through Day 1 (prior to randomization)

CONFIDENTIAL

204947

Table 3 Time and Events Table [Treatment phase 1 (if qualification for re-treatment criteria was met) to treatment phase 2]

Week	Treatment phase 1	Treatment phase 2														With drawal		
		If qualification for re-treatment criteria was met (Within 21days prior to re-treatment)	1st re-treatment	Re-treatment (1st)							If qualification for re-treatment criteria was met (Within 21days prior to re-treatment)	2nd re-treatment	Re-treatment (2nd)					
				2	6	12	18 ^a	24 ^a	30 ^a	Study exit (48 weeks after 1st treatment)			2	6	12 ^a	18 ^a	Study exit (48 weeks after 1st treatment)	
Window	0	± 3 d	± 7 d	± 7 d	± 7 d	± 7 d	± 7 d	± 7 d	± 7 d	± 7 d	0	± 3 d	± 7 d	± 7 d	± 7 d	± 7 d		
Patient characteristics etc.																		
Neutralizing antibody										X							X	X
Efficacy																		
Check of bladder diary ^b	X		X	X	X	X	X	X	X	X		X	X	X	X	X	X	
KHQ, OABSS	X		X	X	X	X	X	X	X	X		X	X	X	X	X	X	
TBS	X		X	X	X	X	X	X	X	X		X	X	X	X	X	X	
Safety																		
Adverse events	X	X	X	X	X	X	X	X	X	X	X	X	X	X	X	X	X	
Physical exam	X										X					X	X	
Height, Weight	X ^c		X ^d	X	X	X	X	X	X	X ^c	X ^c					X ^c	X ^c	
Vital signs	X		X ^e	X	X	X	X	X	X	X	X	X ^d	X	X	X	X	X	
ECG	X ^e															X	X	
Clinical laboratory (hematology and blood chemistry)	X									X	X					X	X	
Urinalysis (dipstick)	X	X ^d	X	X	X	X	X	X	X	X	X ^d	X	X	X	X	X	X	
Urinalysis (clinical laboratory) / Urine culture / sensitivity ^f	X	X ^d	X	X	X	X	X	X	X	X	X ^d	X	X	X	X	X	X	
PVR	X		X	X	X	X	X	X	X	X		X	X	X	X	X	X	
Ultrasound (kidney/bladder)	X ^e											X	X	X	X	X	X	
Pregnancy test (Only females of reproductive potential) ^g	X	X ^d	X	X	X	X	X	X	X	X	X ^d	X	X	X	X	X	X	

CONFIDENTIAL

204947

Week	Treatment phase 1 If qualification for re-treatment criteria was met (Within 21days prior to re-treatment)	1st re-treatment	Treatment phase 2										With drawal			
			Re-treatment (1st)								If qualification for re-treatment criteria was met (Within 21days prior to re-treatment)	Re-treatment (2nd)				
			2	6	12	18 ^a	24 ^a	30 ^a	Study exit (48 weeks after 1st treatment)	2nd re-treatment		2	6	12 ^a	18 ^a	Study exit (48 weeks after 1st treatment)
Window	0	± 3 d	± 7 d	± 7 d	± 7 d	± 7 d	± 7 d	± 7 d	± 7 d	0	± 3 d	± 7 d	± 7 d	± 7 d	± 7 d	
Investigational product																
Treatment of antibiotic ^h		X									X					
Confirmation of day of re-treatment criteri ⁱ		X									X					
Treatment of investigational product		X ^j									X ^j					
Confirmation of qualification for re-treatment criteri ^{i,k}			X	X	X	X	X	X	X	X	X	X	X	X	X	
Concomitant meds / therapies	X	X	X	X	X	X	X	X	X	X	X	X	X	X	X	

d = day (s)

(a) Visit should not have occurred later than 48 weeks after 1st treatment. At 48 weeks after 1st treatment, study exit visit will be conducted.

(b) Bladder diary must have been completed for any 3 consecutive days in the week prior to the visit. The volume voided is recorded by subjects for one 24-hour period during the 3 day diary collection period.

(c) Measured only body weight

(d) Performed prior to treatment

(e) These examination can be completed at the Qualification for re-treatment visit or at any time prior to re-treatment

(f) Urine culture and sensitivity is performed by the central laboratory when urinalysis (dipstick) results were suggestive of a urinary tract infection

(g) If the result of urine pregnancy is suspicious, investigator (or sub-investigator) is able to conduct serum pregnancy test by central laboratory.

(h) First dose to be administered 1 (approximately 24 hours) to 3 days prior to study injection and continued for 1 to 3 days post injection (including the day of injection)

(i) Subjects who are not retreated will continue to visit at the scheduled study visit.

(j) Re-treatment must be occurred after a minimum of 12 weeks (84 days) have elapsed since the previous treatment. Re-treatment should not have occurred later than 36 weeks after 1st treatment

(k) If qualification for re-treatment criteria was met, the patient will undergo the exams specified in Table 2, column marked "If qualification for re-treatment criteria was met"

CONFIDENTIAL

204947

